### **Appendix 3. Medications or Substances Prohibited or to be used with Caution During Study Treatment with Mocetinostat**

**Bold font** indicates medications or substances that might be relatively commonly used.

*Italic font* indicates medications for indications that are exclusionary for the current study or would likely result in discontinuation from study treatment with mocetinostat for management of a concurrent illness.

#### **DRUGS THAT MAY PROLONG QT INTERVAL**

##### **Drugs Prohibited During Treatment with Mocetinostat**

Drugs with a Known Risk of Torsades de Pointes
	
Amiodarone, anagrelide, arsenic trioxide, astemizole (off US market), azithromycin, bepridil (off US market), chloroquine, chlorpromazine, cisapride (off US market), citalopram, clarithromycin, cocaine, disopyramide, dofetilide, domperidone (not on US market), dronedarone, droperidol, erythromycin, escitalopram, flecainide, halofantrine, haloperidol, ibutilide, levomethadyl (off US market), mesoridazine (off US market), methadone, moxifloxacin, ondansetron, pentamidine, pimozone, probucol (off US market), procainamide, quinidine, sevoflurane, sotalol, sparfloxacin (off US market), sulpiride (not on US market), terfenadine (off US market), thioridazine, vandetanib.

---	---

##### **Drugs To Be Used with Caution During Treatment with Mocetinostat**

Drugs with a Conditional Risk of Torsades de Pointes
	
Amantadine, amisulpride, amitriptyline, amoxapine, chloral hydrate, ciprofloxacin, clomipramine, desipramine, diphenhydramine, doxepin, fluconazole, fluoxetine, furosemide, galantamine, hydrochlorothiazide, imipramine (melipramine), indapamide, itraconazole, ivabradine, ketoconazole, metronidazole, nelfinavir, nortriptyline, paroxetine, posaconazole, protriptyline, quinine sulfate, ritonavir, sertraline, solifenacin, telaprevir, trazodone, trimethoprim-sulfa, trimipramine, voriconazole.

---	---

**CAUTION WHEN TAKING THE FOLLOWING MEDICATIONS AND SUBSTANCES**

Enzyme	
Inhibitor of CYP 2E1	Disulfiram
Inducers of CYP 2E1	Ethanol, isoniazid, tobacco
Strong Inhibitors of CYP 3A4	Boceprevir, clarithromycin, conivaptan, grapefruit juice, indinavir, itraconazole, ketoconazole, lopinavir/ritonavir, mibefradil (withdrawn from US market), nefazodone, nelfinavir, posaconazole, ritonavir, saquinavir, telaprevir, telithromycin, voriconazole
Strong Inducers of CYP 3A4	Carbamazepine, phenytoin, rifampin
Substrates of CYP 2C9	Celecoxib, diclofenac, fluvastatin, glipizide, ibuprofen, irbesartan, losartan, naproxen , phenytoin, piroxicam, rosiglitazone, sulfamethoxazole, tamoxifen , tolbutamide, toseamide

#### Appendix 4. Management of Specific Immune-Related Adverse Events

Pneumonitis/ILD		

Monitor patients for signs and symptoms of pneumonitis or ILD (new onset or worsening shortness of breath or cough). Patients should be evaluated with imaging and pulmonary function tests including other diagnostic procedures as described below.
 
Initial work-up may include clinical evaluation, monitoring of oxygenation via pulse oximetry (resting and exertion), laboratory work-up and high-resolution CT scan.
		
Grade of AE	Dose Modifications	Toxicity Management

Grade 1  (Asymptomatic, clinical or diagnostic observations only, intervention not indicated)
	
 
None required.
 
Consider holding as clinically appropriate and during diagnostic work-up for other etiologies
 
	
 
Monitor, follow up in 2-4 days for clinical symptoms, pulse oximetry (resting and exertion) and laboratory work-up and then as clinically indicated
 
Consider pulmonary and infectious disease consult
 


Grade 2  (Symptomatic, medical intervention indicated, limiting instrumental ADL)
	
 
Hold until <math>\leq</math> Grade 1
 
If worsens, treat as Grade 3 or Grade 4
 
If improves to <math>\leq</math> Grade 1, decision to reinstitute study drug/regimen based on clinical judgment and after completion of steroid taper.
 
	
 
Monitor daily and consider hospitalization
 
Promptly start systemic steroids (e.g., prednisone 1-2mg/kg/day or IV equivalent)
 
Reimage as clinically indicated
 
If no improvement within 3-5 days, consider additional workup and prompt treatment with IV methylprednisolone 2-4 mg/kg/day started
 
If still no improvement within 3-5 days despite IV methylprednisone, promptly start immunosuppressive therapy such as TNF inhibitor (e.g. infliximab at 5 mg/kg every 2 weeks). Caution: Important to rule out sepsis and refer to infliximab label for general guidance before using infliximab
 
Once improving, gradually taper steroids over <math>\geq</math> 28 days and consider prophylactic antibiotics, antifungal or anti PCP treatment (refer to current NCCN guidelines for treatment of cancer-related infections (Category 2B recommendation, ASCO Educational Book 2015. Michael Postow MD. “Managing Immune Checkpoint Blocking Antibody Side Effects”)
 
Consider pulmonary and infectious disease consult
 
Consider as necessary discussing with study physician
 


Grade 3 or 4  (Grade 3: Severe symptoms; limiting self-care ADL; oxygen indicated;
 
Grade 4: life threatening respiratory compromise, urgent intervention indicated [e.g. tracheostomy or intubation])
	
 
Permanently discontinue
 
	
 
Promptly initiate empiric IV methylprednisolone 1 to 4 mg/kg/day or equivalent
 
Obtain pulmonary and infectious disease consult
 
Hospitalize the patient
 
Supportive Care (oxygen, etc.)
 
If no improvement within 3-5 days, additional workup should be considered and prompt treatment with additional immunosuppressive therapy such as TNF inhibitors (e.g. infliximab at 5mg/kg every 2 weeks dose) started. Caution: rule out sepsis and refer to infliximab label for general guidance before using infliximab
 
Once improving, gradually taper steroids over <math>\geq</math> 28 days and consider prophylactic antibiotics, antifungals and in particular, anti PCP treatment (refer to current NCCN guidelines for treatment of cancer-related infections (Category 2B recommendation)
 

#### Appendix 4 Management of Specific Immune-Related Adverse Events (Continued)

Diarrhea/ Enterocolitis		

 
Monitor for symptoms that may be related to diarrhea/enterocolitis (abdominal pain, cramping, or changes in bowel habits such as increased frequency over baseline or blood in stool) or related to bowel perforation (such as sepsis, peritoneal signs and ileus)
 
Patients should be thoroughly evaluated to rule out any alternative etiology (e.g., disease progression, other medications, infections including testing for clostridium difficile toxin, etc.)
 
Steroids should be considered in the absence of clear alternative etiology, even for low grade events, in order to prevent potential progression to higher grade event
 
Use analgesics carefully; they can mask symptoms of perforation and peritonitis
 
		
Grade of AE	Dose Modifications	Toxicity Management
Grade 1 diarrhea (stool frequency of < 4 over baseline per day)	
 
None required
 
	
 
Monitor for worsening symptoms
 
Consider symptomatic treatment including hydration, electrolyte replacement, dietary changes (e.g., American Dietetic Association colitis diet), and loperamide. Use of probiotics per clinical judgment.
 

Grade 2 diarrhea (stool frequency of 4-6 over baseline per day)	
 
Hold until resolution to <math>\leq</math> Grade 1
 
If worsens treat as Grade 3 or Grade 4
 
If improves to <math>\leq</math> Grade 1, study drug/study regimen can be resumed after completion of steroid taper.
 
	
 
Consider symptomatic treatment including hydration, electrolyte replacement, dietary changes (e.g., American Dietetic Association colitis diet), and loperamide and/or budesonide
 
Promptly start prednisone 1 to 2 mg/kg/day PO or IV equivalent
 
If not responsive within 3-5 days or worsens despite prednisone at 1-2 mg/kg/day PO or IV equivalent, GI consult should be obtained for consideration of further workup such as imaging and/or colonoscopy to confirm colitis and rule out perforation, and prompt treatment with IV methylprednisolone 2-4mg/kg/day started.
 
If still no improvement within 3-5 days despite 2-4mg/kg IV methylprednisolone, promptly start immunosuppressives such as (infliximab at 5mg/kg once every 2 weeks). Caution: Important to rule out bowel perforation and refer to infliximab label for general guidance before using infliximab
 
Consult study physician if no resolution to <math>\leq</math> Grade 1 in 3-4 days
 
Once improving, gradually taper steroids over <math>\geq</math> 28 days and consider prophylactic antibiotics, antifungals and anti PCP treatment (refer to current NCCN guidelines for treatment of cancer-related infections [Category 2B recommendation])
 

Grade 3 or 4 diarrhea  (Grade 3: stool frequency of $\geq$ 7 over baseline per day;  Grade 4: life threatening consequences)	
 
Permanently discontinue
 
	
 
Promptly initiate empiric IV methylprednisolone 2 to 4 mg/kg/day or equivalent
 
Monitor stool frequency and volume and maintain hydration
 
Urgent GI consult and imaging and/or colonoscopy as appropriate
 
If still no improvement within 3-5 days of IV methylprednisolone 2-4 mg/kg/day or equivalent, promptly start further immunosuppressives (e.g. infliximab at 5 mg/kg once every 2 weeks).
 
Caution: Ensure GI consult to rule out bowel perforation and refer to infliximab label for general guidance before using infliximab.
 
Once improving, gradually taper steroids over <math>\geq</math> 28 days and consider prophylactic antibiotics, antifungals and anti PCP treatment (refer to current NCCN guidelines for treatment of cancer-related infections [Category 2B recommendation])
 

#### Appendix 4 Management of Specific Immune-Related Adverse Events (Continued)

Hepatitis (Elevated LFTs)		

 
• Infliximab should not be used for management of Immune Related Hepatitis
 
• Monitor and evaluate liver function test: AST, ALT, ALP and total bilirubin
 
• Evaluate for alternative etiologies (e.g., viral hepatitis, disease progression, concomitant medications)
 
		
Grade of AE	Dose Modifications	Toxicity Management
Grade 1 (AST or ALT > ULN to 3 times ULN and/or TB > 1.5 times ULN)	
 
• None required
 
• If it worsens, treat as Grade 2 event
 
	
 
• For Grade 1 AST or ALT and/or TB elevation
 
• Continue LFT monitoring per protocol
 

Grade 2 (AST or ALT > 3-5 times ULN and/or TB > 1.5-3.0 times ULN)	
 
• Hold dose until Grade 2 resolution to <math>\leq</math> Grade 1
 
• If worsens then treat as Grade 3 or Grade 4
 
• If improves to <math>\leq</math> Grade 1 or baseline resume study drug/study regimen after completion of steroid taper.
 
	
 
• For Grade 2 AST or ALT and or TB elevation - Frequent checking of LFTs (e.g. every 1-2 days) until elevations improving or resolved.
 
• If no resolution in 1-2 days, discuss with study physician.
 
• If event is persistent (> 3-5 days) or worsens, promptly start prednisone 1-2 mg/kg/day PO or IV equivalent.
 
• If still no improvement within 3-5 days despite 1-2 mg/kg/day of prednisone PO or IV equivalent, consider additional workup and prompt treatment with IV methylprednisolone 2-4 mg/kg/day started.
 
• If still no improvement within 3-5 days despite 2-4mg/kg/day of IV methylprednisolone, promptly start immunosuppressives (mycophenolate mofetil). Discuss with study physician if mycophenolate mofetil is not available. Infliximab should NOT be used.
 
• Once improving, gradually taper steroids over <math>\geq</math> 28 days and consider prophylactic antibiotics, antifungals and anti PCP treatment (refer to current NCCN guidelines for treatment of cancer-related infections [Category 2B recommendation])
 

Grade 3 (AST or ALT > 5-20 times ULN and/or TB > 3.0-10 times ULN)	
 
• For elevations in transaminases <math>\leq 8 \times</math> ULN, or elevations in bilirubin <math>\leq 5 \times</math> ULN
 
• Hold dose until resolution to <math>\leq</math> Grade 1 or baseline
 
• Resume if elevations downgrade <math>\leq</math> Grade 1 or baseline within 14 days, and after completion of steroid taper
 
	
 
• For Grade 3 or 4 AST or ALT and/or TB elevation:
 
• Promptly initiate empiric IV methylprednisolone at 1-4 mg/kg/day or equivalent
 
• If still no improvement within 3-5 days despite 1-4 mg/kg/day methylprednisolone IV or equivalent, promptly start treatment with immunosuppressive therapy (mycophenolate mofetil). Discuss with study physician if mycophenolate is not available. Infliximab should NOT be used.
 
• Hepatology consult, abdominal workup, and imaging as appropriate.
 
• Once improving, gradually taper steroids over <math>\geq</math> 28 days and consider prophylactic antibiotics, antifungals and anti PCP treatment (refer to current NCCN guidelines for treatment of cancer-related infections [Category 2B recommendation])
 

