**Table 9: Immune-Related Adverse Events, Overall Management**

Durvalumab Treatment Modification	

Drug administration modifications made to manage potential immune-related AEs are based on severity of treatment-emergent toxicities graded per NCI CTCAE v4.03.
 
In addition criteria for permanent discontinuation based on severity (Appendix 4), permanently discontinue for the following conditions:
 
 
• Inability to reduce corticosteroid to a dose of <math>\leq 10</math> mg of prednisone per day (or equivalent) within 12 weeks after last dose of study drug
 
• Recurrence of a previously experienced Grade 3 treatment-related AE following resumption of dosing.
 
	
Grade 1	No dose modification
Grade 2	
Hold study drug dose until Grade 2 resolution to <math>\leq</math> Grade 1
 
 
• If toxicity worsens then treat as Grade 3 or Grade 4
 
 
Study drug/study treatment can be resumed once event stabilizes to Grade <math>\leq 1</math> and after completion of steroid taper.
 
Patients with endocrinopathies who may require prolonged or continued steroid replacement can be retreated on the following conditions:
 
 
1) the event stabilizes and is controlled,
 
2) the patient is clinically stable as per Investigator or treating physician’s clinical judgment, and
 
3) doses of prednisone are at less than or equal to 10mg/day or equivalent.
 

Grade 3	Depending on the individual toxicity, may permanently discontinue. Refer to guidelines below.
Grade 4	
Permanently discontinue
 
Note: For Grade 3 and above asymptomatic amylase or lipase levels hold study drug/regimen and if complete work up shows no evidence of pancreatitis, may continue or resume study drug/regimen.

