#### Appendix 4 Management of Specific Immune-Related Adverse Events (Continued)

Hepatitis (Elevated LFTs)		

 
• Infliximab should not be used for management of Immune Related Hepatitis
 
• Monitor and evaluate liver function test: AST, ALT, ALP and total bilirubin
 
• Evaluate for alternative etiologies (e.g., viral hepatitis, disease progression, concomitant medications)
 
		
Grade of AE	Dose Modifications	Toxicity Management
Grade 3 (AST or ALT > 5-20 times ULN and/or TB > 3.0-10 times ULN (cont'd))	
 
• Permanently discontinue if the elevations do not downgrade to <math>\leq</math> Grade 1 or baseline within 14 days
 
• For elevations in transaminases <math>> 8 \times</math> ULN or elevations in bilirubin <math>> 5 \times</math> ULN, discontinue
 
• Permanently discontinue for any case meeting Hy's law criteria (AST and/or ALT <math>> 3 \times</math> ULN + bilirubin <math>> 2 \times</math> ULN without initial findings of cholestasis (i.e. elevated alkaline P04) and in the absence of any alternative cause
 
• (FDA Liver Guidance Document 2009 Guidance for Industry: Drug Induced Liver Injury – Premarketing Clinical Evaluation NCI CTCAE version 4.03)
 
	See above.
Grade 4 (AST or ALT > 20 times ULN and/or TB > 10 times ULN)	
 
• Permanently discontinue
 
	

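### The Grade 1 bilirubin limit in the hepatitis dosing table has no ceiling and shares Grade 2's floor, so an isolated bilirubin above 1.5 and up to 5 × ULN meets both a no-change row and a hold row

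*Protocol*

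**What the plan says.** The hepatitis (elevated LFTs) table in Protocol Appendix 4 gives numeric bands for each grade and a dosing action for each band.

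- **Grade 1** is "AST or ALT > ULN to 3 times ULN and/or TB > 1.5 times ULN". No dose modification is needed, and the management column says "Continue LFT monitoring per protocol". A further line tells the site to move to Grade 2 handling if the event worsens.
- **Grade 2** is "AST or ALT > 3-5 times ULN and/or TB > 1.5-3.0 times ULN". The dose is held until the event falls to Grade 1 or lower, and LFTs are checked often, for example every 1 to 2 days.
- **Grade 3** is "AST or ALT > 5-20 times ULN and/or TB > 3.0-10 times ULN". Up to 5 × ULN for bilirubin the dose is held and IV methylprednisolone is started. The restart rule begins "Resume if elevations downgrade" and requires Grade 1 or lower, or baseline, within 14 days and a completed steroid taper. Its counterpart begins "Permanently discontinue if the elevations do not downgrade to" and uses the same target and the same 14 days. Above 5 × ULN the drug is discontinued.
- **Grade 4** is bilirubin above 10 × ULN (or AST/ALT above 20 × ULN), with permanent discontinuation.

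Table 9 of the protocol bases irAE modifications on "severity of treatment-emergent toxicities graded per NCI CTCAE v4.03". Section 8.2.2 also names CTCAE v4.03 for grading. Neither document prints the CTCAE bilirubin bands.

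**The concern.** The AST/ALT half of the Grade 1 cell is a closed range that ends where Grade 2 begins. The bilirubin half is not: it has a floor of 1.5 × ULN, the same as Grade 2, and no ceiling. Read as printed, the lowest grade takes in every bilirubin value that belongs to the higher grades, and mild elevations just above ULN belong to none.

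Two things are at stake. The first is the immediate action: the same laboratory result supports continuing unchanged or holding both the dose and the schedule. The second is what follows a hold. Grade 1 or lower is the restart target in the Grade 2 and Grade 3 rows and the test for permanent discontinuation at 14 days, and the printed Grade 1 row gives those rules no bilirubin level of its own. Mocetinostat is affected as well, because Section 5.1.8.1 interrupts it for an irAE until Grade 1 or lower and points to Table 9 and Appendix 4 as similar guidance. Hepatitis/hepatotoxicity is a listed durvalumab adverse event of special interest (Section 8.3.3.1).

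**Working it through.** No sample size or error rate is involved. The check is to take the printed bands and list which rows a patient meets when AST and ALT are normal.

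**Inputs** (Appendix 4, hepatitis; TB = total bilirubin in multiples of ULN):

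- Grade 1: TB > 1.5, no change
- Grade 2: 1.5 < TB ≤ 3.0, hold
- Grade 3: 3.0 < TB ≤ 10; hold if TB ≤ 5, discontinue if TB > 5
- Grade 4: TB > 10, permanently discontinue

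**Rows met**

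| TB (× ULN) | As printed | With Grade 1 as 1 < TB ≤ 1.5 |
|---|---|---|
| 1.2 | none | Grade 1, no change |
| 1.5 | none | Grade 1, no change |
| 1.51 | Grade 1 no change; Grade 2 hold | Grade 2, hold |
| 2 | Grade 1 no change; Grade 2 hold | Grade 2, hold |
| 3 | Grade 1 no change; Grade 2 hold | Grade 2, hold |
| 4 | Grade 1 no change; Grade 3 hold | Grade 3, hold |
| 5 | Grade 1 no change; Grade 3 hold | Grade 3, hold |
| 5.01 | Grade 1 no change; Grade 3 discontinue | Grade 3, discontinue |
| 10.1 | Grade 1 no change; Grade 4 discontinue | Grade 4, discontinue |

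The overlap of no change with a hold runs over (1.5, 3.0] against Grade 2, width 3.0 − 1.5 = 1.5, and over (3.0, 5.0] against Grade 3, width 5.0 − 3.0 = 2.0. Together that is (1.5, 5.0], width 3.5 × ULN. Above 5 × ULN the Grade 1 wording still applies on its face, but the explicit numeric stops settle the action.

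**Example 1: first action.** A patient without Gilbert syndrome or liver metastases enters at 1.5 × ULN or below (inclusion criterion 7e) and rises to 2 × ULN. On the Grade 1 reading, dosing continues and the next planned chemistry in Table 1 is 14 days later in Cycles 1 to 3 (Days 1 and 15) or 28 days later from Cycle 4 (Day 1 only). On the Grade 2 reading, the dose is held and LFTs are repeated, for example, every 1 to 2 days.

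**Example 2: restart or stop.** The same patient falls from 4 to 2 × ULN by day 14. If 2 × ULN is Grade 2, the 14-day rule requires permanent discontinuation. If it is Grade 1, dosing may resume after the steroid taper.

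**Inferring the intended limit.** Three features of the table point to a ceiling of 1.5 × ULN: the Grade 2 floor is 1.5; the AST/ALT range in the same cell runs from ULN up to the Grade 2 floor; and the Grade 1 nephritis row in the same appendix gives creatinine as above ULN to 1.5 × ULN. With that ceiling, every value above ULN maps to one action, as the right-hand column shows.

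**The case against.** The strongest reply is that few sites would be misled. An unlimited Grade 1 would contain even Grade 4 values, so the literal reading defeats itself, and taking the higher grade met gives one action at every value above 1.5 × ULN. Table 9 and Section 8.2.2 make CTCAE v4.03 the grading standard. Table 9 holds at Grade 2, and so does Table 11 if the event is not immune-mediated. The Grade 1 row itself sends a worsening event to Grade 2 handling, so a bilirubin that climbs from 2 to 4 × ULN would be held on either reading. The Grade 2 hold lasts until Grade 2 has resolved, which a value of 2 × ULN has not done. Chemistry is planned on each Day 1, so no durvalumab dose falls due without a scheduled test, and Section 7.3.4 allows extra tests.

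Much of this stands as a limit on practical effect, but it does not remove the error. The worsening line gives no bilirubin level and does not cover a first reading already inside the range. The wording about Grade 2 resolution is absent from the Grade 3 restart rule, which governs Example 2. The documents name CTCAE without printing its bilirubin bands, while Section 5.2.8 sends sites to Appendix 4 for the detail by event type and the hepatitis table prints its own numbers. Hy's Law needs raised transaminases, so it does not reach isolated bilirubin.

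The original PDF page could not be seen, so loss of characters in text extraction cannot be fully excluded. The row reads as intact, and the closed AST/ALT range survives in the same cell.

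**Conclusion.** The concern holds. As printed, with normal ALT and AST, bilirubin above 1.5 and up to 5 × ULN meets both a no-change row and a hold row, and the restart and 14-day stop rules inherit the ambiguity. It should be fixed, because it is a wrong threshold in an operative safety table.

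The effect is bounded. Above 5 × ULN and at Grade 4 the printed stops decide, and a Hy's Law case is stopped whatever its grade (Section 8.2.1). Patients with Gilbert syndrome or liver metastases may enter at up to 3.0 × ULN, so 2 × ULN may be their baseline and the baseline alternative then governs restart in the Grade 2 and Grade 3 rows. The DLT definition has its own bilirubin limit of 5 × ULN and names CTCAE v4.03 (Section 3.1.1). The SAP grades laboratory values numerically by CTCAE v4.03 (Section 12.6.8). Trial conclusions are not affected.

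Two assumptions remain: that the extracted row matches the sponsor's page, and that the intended ceiling is 1.5 × ULN, which is inferred from the table and not stated in the documents.

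**What to change.** Change the bilirubin part of the Grade 1 criterion in the Appendix 4 hepatitis table to TB > ULN to 1.5 times ULN. Before doing so, check the row in the original PDF and confirm the band against CTCAE v4.03. The other rows can stay as they are. The cost is one line in one table, with no new tests, visits or patients.

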#### Appendix 4 Management of Specific Immune-Related Adverse Events (Continued)

Hepatitis (Elevated LFTs)		

 
• Infliximab should not be used for management of Immune Related Hepatitis
 
• Monitor and evaluate liver function test: AST, ALT, ALP and total bilirubin
 
• Evaluate for alternative etiologies (e.g., viral hepatitis, disease progression, concomitant medications)
 
		
Grade of AE	Dose Modifications	Toxicity Management
Grade 3 (AST or ALT > 5-20 times ULN and/or TB > 3.0-10 times ULN (cont'd))	
 
• Permanently discontinue if the elevations do not downgrade to <math>\leq</math> Grade 1 or baseline within 14 days
 
• For elevations in transaminases <math>> 8 \times</math> ULN or elevations in bilirubin <math>> 5 \times</math> ULN, discontinue
 
• Permanently discontinue for any case meeting Hy's law criteria (AST and/or ALT <math>> 3 \times</math> ULN + bilirubin <math>> 2 \times</math> ULN without initial findings of cholestasis (i.e. elevated alkaline P04) and in the absence of any alternative cause
 
• (FDA Liver Guidance Document 2009 Guidance for Industry: Drug Induced Liver Injury – Premarketing Clinical Evaluation NCI CTCAE version 4.03)
 
	See above.
Grade 4 (AST or ALT > 20 times ULN and/or TB > 10 times ULN)	
 
• Permanently discontinue
 
	

